At week 2 (the end of the 2-week baseline, in person), participants will hand in scores and be randomized to a frequency. Part of this 60-minute visit will be considered standard of care, a level 3, 20-minute educational visit on a commonly used treatment option. They will be given a TENS unit and taught how to use the unit. Teaching will include positioning of electrodes, as well as what buttons they are allowed to manipulate. The TENS unit settings will be pre-determined at the clinic and measures will be taken to ensure that the settings cannot be altered at home. The participant will be instructed not to open the TENS unit during the 2 treatment weeks of the study to ensure the settings are maintained. They will be instructed to continue only their baseline treatments.

Settings: The TENS unit used is a Compass Health TENS 3000, 3 mode Analog Unit. The participants' TENS unit will be set at Normal Mode (N), a pulse width of 200 microseconds and an intensity to be determined in the office based upon when the participant feels sensitive to the TENS unit. Frequency (pulse rate) will be determined by randomization. The participant will place the electrodes along the posterior tibial nerve on the medial ankle with a ground on the inner arch, each day for 30 minutes for a total of 14 days at the time of day typically associated with the worst pain or at the first opportunity for rest after this time.

Group 1 will be the **low** frequency group. This means that the TENS therapy will use a frequency of 20 Hz.

Group 2 will be the **medium** frequency group. This means that the TENS therapy will use a frequency of 50 Hz.

Group 3 will be the **high** frequency group. This means that the TENS therapy will use a frequency of 100 Hz.

Participants will be provided the TENS unit, its manual, and enough patches to last the 2 weeks of the treatment period. Participants will be given a weekly usage log, weekly pain VAS and weekly GUPI questionnaire logs again for 2 weeks they are actively using the TENS, with the option of paper or Qualtrics. In this log, the rating of pain by VAS and GUPI, the rating of genitourinary symptoms by GUPI, duration of TENS therapy, usage for every day of the week and adverse reactions to the TENS unit (rash) will be recorded.

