prevent nerve accommodation by continuously cycling the treatment intensity. When using Modulated Mode increase the intensity only when the unit is at the maximum intensity of the modulation cycle. If the intensity is increased during a low intensity period of the cycle, the participant may turn up the control very slowly, so that they may feel the intensity any higher.

In a future study we will want to look at Normal (more like massage) versus Modulated mode (more like acupuncture).

C. SUBJECT POPULATION (WHO, WHAT, WHERE)

Inclusion criteria for cases:

1. Age 18-90 years of age seen at Albany Medical Center Division of Urology
2. Presenting with chronic pelvic pain (chronic/persistent pain that has been continuous or recurrent for at least three months (in accordance with EAU Guidelines).
3. Unsuccessful initial interventions based on initial assessments
4. Ability to provide informed consent and complete study requirements
5. Ability to complete a comprehensive history (including with an interpreter)

Exclusion criteria for cases:

1. Participants who have previously tried a new pharmacologic treatment for pelvic pain, neuromodulation or other alternative therapy for urologic disorders within the past 30 days
2. Inability to work a TENS unit
3. Any contraindications to usage of a TENS unit (pacemaker or other implantable device, lymphedema, pregnancy, malignancy, bleeding or clotting disorders, unhealthy tissue, seizure disorders, impaired cognition)
4. Any history of electrophysiologic heart disease or complications
5. Source of pain being an obvious anatomic issue requiring alternative treatment – for example urethral diverticulum, distal ureteric stone.
6. Participant who is pregnant
7. Participant with adhesive allergy either reported by the participant or upon chart review

D. DATA ANALYSIS

The data collection list is attached to the protocol. The data will be collected on a deidentified excel spreadsheet by participant study number and the deidentified data will be entered into the database. The source documents and informed consents will be kept in the locked Urology Research Office. Qualtrics data will be downloaded onto a secure excel spreadsheet that will immediately be uploaded to the secure urology one drive. Paper responses will be entered to this spreadsheet manually.

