Statistical Methods

For the primary objectives:

- Analysis of variance with a fixed effect of treatment with Tukey's multiple comparison test will be used to test for differences in the reduction in genitourinary symptoms among the three treatment arms. Reduction will be parameterized as a relative change from baseline to after the two weeks of treatment. VAS pain response before and after treatment will be compared among the three groups using repeated measures ANOVA with Tukey's multiple comparison tests.
- The Chi-square test or Fisher's exact test, as appropriate, will be used to compare the rates of response among the three treatment arms at the end of the 14-day treatment period.

For the secondary objectives, a repeated measures analysis of variance will be used to analyze the outcomes of interest on a week-to-week basis (improvement in GUPI scores). A treatment-by-time interaction will be examined to determine if the patterns of change in GUPI and VAS scores over time differ across groups. Adjusted pairwise comparisons (Tukey or Bonferroni method) will be used to compare treatment groups to one another.

Data transformations may be applied, if necessary, in order to meet the required standard model assumptions.

Sample Size Considerations

Power: The number of participants needed was based on a power calculation (ANOVA with 2-tailed alpha of 0.05) assuming that the minimally important difference to detect among the three groups in the change in VAS score would be at least one within-group standard deviation of the change in score at 14 days. With 21 participants per group the power is estimated at 81%. We propose to randomize 25 per group assuming the dropout rate may be as high as 20%.

Based on investigator expertise and some published studies, we assume that the proportions of responders based on our criteria of a “favorable response” for each of the three TENS groups will be around 40 % (1,2,4,7,10). In our study we are aiming for at least a 40% response rate in our complex and refractory population.

Conduct of the study

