Participants with contraindications to TENS (eg, other electrical devices, pregnancy, bleeding or clotting disorders, unhealthy tissue, seizure disorders, malignancy, impaired cognition, adhesive allergy) will be excluded from the study. Participants will be taught safe practice with the use of a TENS unit, such as performing a sensory discrimination test in the office, checking and cleaning skin before starting a TENS session, monitoring skin for signs of irritation, changing adhesive on electrode pads after each use, securing electrodes with even pressure distribution and full contact, and watching for signs of TENS unit malfunction requiring maintenance [11].

Participants will be instructed to adjust the intensity to the level they can tolerate, so if the TENS intensity is too high then the participants will not be able to tolerate. Pain is the main issue with increased intensity (when it is not used to actually treat pain), therefore intensity will be minimized as per protocol to prevent this (“to the participant’s perception and tolerance”). Increased intensity would be assumed to lead to skin break down, however, reports of this are exceedingly rare (13). Participant education will be comprehensive here.

While reports of dermatitis have been reported in the literature, in most of these cases the dermatitis is caused by an allergy to the adhesive on the TENS electrode pads and not the actual electrical stimulation. Skin irritation can occur, but this is mostly seen in cases where TENS therapy has been used for multiple hours in a row. There has been only one case report in the literature (and not even searchable in Pubmed) of an actual burn from a TENS unit (14). In contrast, TENS therapy is actually used for pain relief on burn participants. Therefore, the risk of being burned from TENS therapy is extraordinarily low.

The effects of prolonged TENS usage have been studied in the literature before. The meta-analysis by Mark Johnson et al showed TENS units to be very safe with very few adverse effects seen even for more extended periods of use (10)

E. RISKS

The risks are minor and unanticipated. If there is any irritation to the participants skin due to the adhesive pads the participant will be treated and taken off the study.

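### The Week 2 text randomises before the unit is handed over and taught, and nothing requires device ability or visible skin condition to be confirmed before the envelope is opened

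*Combined protocol and SAP*

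**What the plan says.** Section B, Study Procedures, describes the Week 2 visit in this order: "participants will hand in scores and be randomized to a frequency"; then, after a sentence on billing, "They will be given a TENS unit and taught how to use the unit". Intensity is set for each participant at the office, but its order relative to setting the frequency is not given.

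The Section C exclusions include "Inability to work a TENS unit" (no. 2) and, among the device contraindications (no. 3), unhealthy tissue. Neither has a stated time or method of assessment. Section D, Conduct of the study, lists safe practices that participants are taught, "such as performing a sensory discrimination test in the office" among them, along with checking the skin before a session.

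Four other places bear on the timing:

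- The Week 1 screening text (Section B) allows a virtual contact and ties randomisation only to the pain or quality-of-life threshold.
- The schedule marks Week 2 as in person only. It is the first such visit, and its row does not tick the Treatment Map, although the rows for Weeks 1, 3 and 4 do.
- Section D, Randomization, has the sealed envelope opened once a subject is enrolled. The baseline text in Section B places enrolment before the baseline week.
- Section D, Intention-to-treat, admits a participant to that analysis only with at least eight documented sessions.

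**The concern.** Eligibility should be settled before allocation, because after it every removal is a post-randomisation exclusion. Followed literally, the Week 2 text gives a participant an arm before the first described hands-on contact with the device. Someone who then cannot operate it, or whose skin turns out to be unsuitable, has already been randomised. The plan has no rule for that person, and the eight-session condition would take them out of the primary analysis by default.

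Two things are at stake. One is precision, in a trial with 25 per arm and little slack. The other, which matters more, is that the groups compared would no longer be the groups randomised. A check made before the envelope is opened avoids both for every failure it can detect.

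**Working it through.** **Timing: the relevant texts side by side.**

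1. The Week 2 paragraph places randomisation at the handing-in of scores and describes teaching afterwards.
2. The Week 1 paragraph can be read as randomising once the pain threshold is met, which is earlier still.
3. The envelope rule depends on enrolment, and enrolment comes before the baseline week. It therefore does not ensure that anything done at the Week 2 visit precedes allocation.
4. A phone or mail recruit need not be seen in person before Week 2, so skin cannot be inspected earlier. Section B also excludes people reporting prior TENS use, so ability can rarely be inferred from experience.
5. The urine pregnancy test follows consent but has no stated place relative to allocation.

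No text puts exclusion 2, or the visible part of exclusion 3 for remote recruits, ahead of the envelope.

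**Consequence under the plan's own rule.** A participant found unable or unsuitable at teaching would not be expected to document eight sessions, and so would leave the intention-to-treat set.

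**Size: the plan's power figure first.** Inputs from Section D, Sample Size Considerations: "ANOVA with 2-tailed alpha of 0.05"; a difference of "at least one within-group standard deviation of the change in score at 14 days"; "With 21 participants per group the power is estimated at 81" percent; and "We propose to randomize 25 per group assuming the dropout rate may be as high as 20" percent. The pattern of the three means is not stated. I assume −0.5, 0 and +0.5 SD.

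Power = P(F′ > F₀.₉₅), where F′ is noncentral F with 2 and 3(n − 1) degrees of freedom and noncentrality λ = n × (0.25 + 0 + 0.25) = 0.5n.

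| n per arm | λ | df | power |
|---|---|---|---|
| 21 | 10.5 | 2, 60 | 0.815 |
| 20 | 10.0 | 2, 57 | 0.793 |
| 19 | 9.5 | 2, 54 | 0.770 |
| 18 | 9.0 | 2, 51 | 0.744 |

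The stated 81% at 21 per arm is reproduced. Successive losses are 2.2, 2.3 and 2.6 points, so about 2 to 2.5 points per participant per arm. If instead two means are equal and the third lies 1 SD away, power is 0.915 at 21, 0.900 at 20 and 0.863 at 18, and the loss is 1.5 to 2 points per participant.

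**Slack.** 25 × (1 − 0.20) = 20, one below the planned 21. Keeping 21 of 25 corresponds to 16% dropout.

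**Range for late exclusions.** The documents give no rate. Let x be an assumed proportion lost to late eligibility findings on top of dropout d, so that n = 25 × (1 − d) × (1 − x), using the first pattern of means:

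| x | n at d = 16% | power | n at d = 20% | power |
|---|---|---|---|---|
| 0% | 21.0 | 0.815 | 20.0 | 0.793 |
| 4% | 20.2 | 0.797 | 19.2 | 0.775 |
| 10% | 18.9 | 0.767 | 18.0 | 0.744 |

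The documents contain nothing from which a bias could be computed.

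**The case against.** The strongest reply is that the late timing is inferred from sentence order. The Week 2 paragraph is not a strict sequence, since its next sentence concerns billing. The recruitment text in Section B lists people who cannot work a unit among those excluded, and Conduct of the study mentions excluding contraindications before it turns to teaching. A site could follow every sentence and still confirm Section C first. Exclusion 2 prescribes no hands-on test, so history or interview might serve. This stands as far as it goes: the documents do not say that the checks follow allocation. But nothing requires them to come first, and the only sequence written down points the other way.

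Four further objections also carry weight:

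- **Sensory test.** A reader might treat it as a ground for exclusion. The plan presents it as safety teaching and attaches no exclusion to its result.
- **Arm-related loss.** A reader might infer that staff who know the arm judge ability with a unit already set to the assigned frequency. The plan blinds participants and caretakers only, but it does not say who teaches or whether the frequency is set beforehand. Handling a device and skin condition have no evident link to 20, 50 or 100 Hz.
- **Dropout allowance.** The 20% is given as an upper figure and could already include these losses.
- **Treatment Map.** A treatment begun in the lead-in may be a protocol deviation rather than an eligibility failure, and Section B has the Map kept up throughout the study. The missing Week 2 tick is a minor supporting point.

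**Conclusion.** The point holds as a gap in sequence with a defined consequence. The written order is randomise, then teach. No text places confirmation of exclusion 2, or of visible skin condition in remote recruits, before allocation. The eight-session condition turns a late finding into a loss from the primary analysis.

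The cost in power is modest: about 2 to 2.5 points per participant per arm near 20, under equally spaced means with a 1 SD range. The number of such participants is unknown, and the 0 to 10% range is an assumption. The planned power figure itself is not in dispute. The main reason to act is to protect the randomised comparison.

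Two stronger readings are not supported. One is that the trial will be biased by arm-related exclusions: this can be neither shown nor ruled out from the documents. The other is that reordering would remove all such losses. It removes only failures detectable before stimulation. A teach-back with the unit off cannot reveal intolerance of the assigned stimulation, which is the more plausible arm-related route. That is why the analysis-set rule has to change as well as the order.

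**What to change.** 1. In the Week 2 text of Section B, fix the order within the existing 60-minute visit: collect the Week 1 and 2 scores; update the Treatment Map; do the skin check and a teach-back with the unit off; confirm and document all Section C exclusions; only then open the envelope and set the frequency.
2. Tick the Treatment Map at Week 2 in the schedule.
3. Reconcile the Week 1 screening text, the Week 2 text and the Randomization section so that they give one time of randomisation, and tie the envelope to documented eligibility rather than to enrolment alone.
4. In Section D, state that everyone randomised stays in the intention-to-treat analysis whatever is found later and however many sessions are used. Keep the eight-session rule for the per-protocol set.

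The cost is slightly longer work before allocation in a visit that already exists, with no added visit. Item 4 also means still collecting the Week 3 and 4 questionnaires from participants who do not use the device.

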All subjects will be analyzed according to the intention-to-treat [ITT] principle. A participant will be considered evaluable and will be included in the intention-to-treat analysis if the participant has documented at least 8 sessions of their designated TENS treatment (about 4 times a week of TENS therapy). Analyses that take into account the actual treatment received (e.g., non-compliance, etc.) will be carried out as a secondary analysis (per protocol [PP] analysis).

Primary Statistical Objective:

The primary objective of the study is to compare the three TENS treatment groups after two weeks of active treatment, with respect to:

The change in VAS and GUPI pain questionnaires from baseline to after two weeks of

therapy.

The proportion of responders after two weeks of therapy.

Secondary Statistical Objectives:

Secondary objectives include comparison of the three treatment groups with respect to the rating of VAS and GUPI scores, separately, over time (by weekly diary entries). Analysis will be carried out to determine if there are time-dependent changes in questionnaire scores across the three TENS treatment groups. Urinary symptoms and individual pain site questions will be noted.

Pairwise comparisons of TENS groups will also be carried out to compare each arm with one another using Tukey's multiple comparison tests.

We will again collect data at 1,2-, and 3-months post-trial, asking how much the TENS has been used, to assess durability.

Outcome Variables and Schedule of Assessments:

The primary outcome variable of interest is participant's percentage change in VAS and GUPI from before treatment to the end of 2 weeks of active TENS. Also evaluated will be the response to treatment each week during the 14-day TENS therapy period and the 2 weeks of observation. A participant is said to have a favorable response to the treatment if he/she has a decrease of at least 2 points on the VAS or 1 point on the GUPI question #9 from baseline to after two weeks of TENS therapy. Change in outside interventions will not be permitted during the study but stable therapies will be maintained (e.g., medications).

Demographics and participant characteristics will be collected at baseline (age, gender, medical history, surgical history, current medications, site of pain, duration of chronic pelvic pain). The following outcomes will be measured at baseline, at each week, and at 3 months after the TENS therapy month:

- VAS Weekly Scores
- GUPI Weekly Scores

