The principal investigator, [name] MD, is responsible for overall oversight of the data, monitoring the data, assuring protocol compliance, and conducting the safety reviews. The principal investigator will also be responsible for compiling the data sheets, day to day oversight of research and ensuring the integrity and privacy of the data. During the review process the principal investigator, along with the other investigators, will evaluate whether the study should continue unchanged, require modification/amendment, or close to enrollment. The principal investigators or the Institutional Review Board (IRB) have the authority to stop or suspend the study or require modifications.

The master key will house PHI relating to name, address, phone number, MR number and date of birth. The secure Qualtrics survey obtained weekly from participants will be securely downloaded as an excel spreadsheet into a protected AMC Onedrive file accessible only to study personnel. This spreadsheet will be uploaded directly to the secure one drive account to ensure participant confidentiality and security of PHI. Paper surveys will be entered into this database within Onedrive. The master key and database will be stores in separate protected Onedrive files.

Any worsening symptoms or adverse reactions will be reported to the examiners, by way of pain questionnaire, phone calls to participants, the 14-day clinic visits, or reported by participants aside from these instances. For participants with any severe or persistently worsening symptoms or adverse reactions, TENS therapy will be immediately discontinued, they will be removed from the study and considered to have failed treatment and receive medical treatment as necessary. Skin irritation is the most common adverse reaction to TENS units; however, this is mostly associated with allergy to the self-adhesive electrodes (12). While pain may be a

complication with TENS, studies have shown TENS is actually beneficial in treatment of pain over different areas of the body (12).

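### The set labelled intention-to-treat admits only participants with at least 8 logged sessions, so early stoppers, including declared treatment failures, drop out of the primary analysis

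*Combined protocol and SAP*

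**What the plan says.** The Intention-to-treat paragraph of section D opens with "All subjects will be analyzed according to the intention-to-treat [ITT] principle". The next sentence restricts that analysis: "A participant will be considered evaluable and will be included in the intention-to-treat analysis if the participant has documented at least 8 sessions". A per-protocol analysis by treatment actually received follows as secondary.

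Four other places bear on this:

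- **Timing of randomisation** (section B, week 2 visit): at the end of the two-week baseline, "participants will hand in scores and be randomized to a frequency". No TENS session has taken place by then.
- **Session schedule** (section B, Settings): "each day for 30 minutes for a total of 14 days".
- **Stopping for harm** (section D, Conduct of the study): where symptoms or reactions are severe or keep getting worse, the plan says "TENS therapy will be immediately discontinued, they will be removed from the study and considered to have failed treatment".
- **Skin irritation** (section E, Risks): "If there is any irritation to the participants skin due to the adhesive pads the participant will be treated and taken off the study".

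Sample Size Considerations allows for losses: "We propose to randomize 25 per group assuming the dropout rate may be as high as 20" per cent. The plan gives no all-randomised analysis, no method for missing scores and no sensitivity analysis for them.

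**The concern.** The two sentences of the Intention-to-treat paragraph contradict each other. The second makes membership depend on what participants do and write down after randomisation. The rule says 'if' rather than 'only if', but as a definition of who is evaluable it has no other sensible reading.

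It also collides with the Conduct of the study section. A person stopped for worsening in the first week is declared a failure there, yet is absent from the analysis that should count the failure. The rule discards observed data too: someone with 7 logged sessions and complete week 4 scores is left out.

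The trial's purpose is to rank three frequencies, and there is no sham arm. If one frequency leads more people to stop early, and those people do worse, its poorest results disappear and it can look best. Even with equal stopping, reported response rates are too high whenever stoppers respond less often than those who continue.

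**Working it through.** **Inputs from the plan:** 14 daily sessions; threshold 8; 25 randomised per arm; dropout up to 20%; assumed response about 40% in each arm; one-way ANOVA at alpha 0.05; 21 per arm for 81% power at a difference of 1 within-group SD.

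**Assumptions:** number of early stoppers in each arm; their response rate; that the 20% dropout all falls below 8 sessions.

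**1. The plan's own power figure.** Noncentral F, three arms, means 0, 0.5 and 1 SD. The noncentrality is n × Σ(mean − grand mean)² = 21 × 0.5 = 10.5, with 2 and 60 df. Power is 81.5% against the stated 81%, so it reproduces. With 25 × 0.80 = 20 left per arm it is 79.3%.

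**2. Who is excluded for certain.** The threshold is 8/14 = 57% of sessions. Stopping by treatment day 7 gives at most 7 sessions, and 7 < 8.

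**3. Response rates.** True responders per arm: 0.40 × 25 = 10. If the s stoppers in an arm are all non-responders, the observed rate is 10/(25 − s):

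- s = 0: 10/25 = 40%
- s = 1: 10/24 = 42%
- s = 3: 10/22 = 45%
- s = 5: 10/20 = 50%

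**4. Responder test with no true difference.** Exact enumeration: responders in each arm are binomial with size 25 − s and probability 10/(25 − s). The test is Pearson chi-square, 2 df, alpha 0.05, with ties for first place split.

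| Stoppers by arm | Stoppers' response | Rejection | Arm with most stopping ranks first |
|---|---|---|---|
| 0/0/0 | – | 4.9% | 33% |
| 5/5/5 | 0% | 5.0% | 33% |
| 2/3/4 | 0% | 5.6% | 42% |
| 1/3/5 | 0% | 7.6% | 51% |
| 0/3/5 | 0% | 9.3% | 53% |
| 0/5/5 | 0% | 10.4% | two arms tie |
| 1/3/5 | 20% | 5.8% | 42% |
| 0/5/5 | 20% | 6.6% | two arms tie |

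If stoppers respond at 40%, rejection is about 5%. An assumed 1/3/8 split, beyond the 20% ceiling in one arm, gives 15.5% and 73%. The test on all randomised participants stays at about 5% throughout.

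**5. Mean-change ANOVA with no true difference.** Simulation with 5 of 25 removed in one arm and none in the others. The correlation between stopping and poor outcome is assumed to be 0.5, 0.8 or 1.0.

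- That arm's mean is inflated by 0.17, 0.27 or 0.34 SD.
- Rejection is about 8%, 14% or 22%, against about 5% with everyone included.
- With 5 removed in every arm the mean bias is about zero. Rejection still rose to 5.8%, 9.1% and 12.4%, but this comes from removing exactly the five lowest-ranked people per arm. When each person instead stops below a fixed cut-off (20% on average), equal stopping gives about 5%, and stopping in one arm only gives about 8%, 14% and 20%.

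**The case against.** The strongest reply is that nothing in the plan shows stopping will differ by frequency, and some features point the other way. Pads, site and session length are the same in all arms, intensity is set to each person's tolerance, participants are blinded, and irritation is attributed mainly to adhesive allergy. Bias between arms also needs stopping to be related to outcome, not merely to differ by arm. The larger figures assume that stoppers never respond and that all dropout falls below 8 sessions; milder cases within the 20% ceiling give about 5% to 7%. All of this stands, and it limits the size of the problem. It does not remove the contradiction. The link to outcome is also likely for people stopped under the Conduct of the study section, who are failures by definition.

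A second reply is that people removed from the study would usually have no week 4 score, so the ANOVA would lose them whatever the set is called. This is right: the 8-session filter and missing scores are two separate losses. The filter alone costs the ANOVA those with few logged sessions but a week 4 score. Redefining the set does not recover the others, so data collection after stopping must be addressed as well.

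Third, people with pad irritation may already count as failures, since the Conduct of the study section treats skin irritation as an adverse reaction. That reading is possible. However, that section speaks of severe or persistently worsening cases and the Risks section of any irritation, so the plan does not settle it.

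**Conclusion.** The concern holds, and the definition should be corrected before any analysis. The contradiction within the Intention-to-treat paragraph, and the certain exclusion of anyone who stops within the first 7 treatment days, follow from the text and rest on no assumption. The definition governs both primary comparisons.

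The size is conditional. Within the plan's 20% dropout ceiling, false rejection of the responder test runs from about 5% (stopping equal across arms, or unrelated to outcome) to about 10% (0/5/5 stoppers, none responding). Observed response can rise from 40% to as much as 50%. For mean change, an arm that alone loses 5 of 25 could gain 0.17 to 0.34 SD. The plan gives no stopping rates by arm, so these are ranges, not forecasts.

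**What to change.** 1. Define the intention-to-treat set as all randomised participants, analysed as assigned, whatever number of sessions they log.
2. Use the 8-session threshold only to define the per-protocol set.
3. In the responder analysis, count those declared failures under Conduct of the study as non-responders, and state how those taken off for skin irritation are counted.
4. Reconcile removal from the study in Conduct of the study and in section E with data collection, so that week 3 and week 4 VAS and GUPI are still requested from people who stop TENS. This concerns data only and changes no clinical stopping rule.
5. Name one method for scores that remain missing, plus a sensitivity analysis that does not assume missing at random.

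The cost is wording in sections D and E; the questionnaires already exist on paper and by Qualtrics link. Reported response falls, from 50% to 40% in the 20% illustration. Power may fall too. If 20% in each arm stop and gain nothing, a range of 1.0 SD becomes 0.8 × 1.0 = 0.8 SD. Power with 25 per arm is then 69.8% with the SD held at 1. It is about 66.8% if the variances rise to 1, 1.04 and 1.16 through mixing stoppers with the rest. The filtered set of 20 per arm gives 79.3%, but only for a selected subgroup, so it does not justify keeping the filter. If stoppers keep the full benefit and everyone has an outcome, 25 per arm gives 88.3%.
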